5.2.6. TumorAssessment Date

Tumor assessment dates will be assigned differently for ICR assessment and for investigator's assessment of tumor data.

For analyses of ICR assessments, the date of tumor assessments will be determined based on the radiologist assessments at each nominal timepoint and will be provided on listings as the associated date of response/progression at nominal timepoints. These dates will also be used for censoring in time to event analyses; however, the date of progression and response as provided by ICR will be used in time to event endpoint analyses as the independent oncologist provided an overall assessment of best response and date of progression based on a review of each nominal timepoint and additional clinical information available for the determination of the date of response/progression.

For analyses based on investigator's assessment when response/progression are derived programmatically from the target lesions measurements, non-target lesions status, and new lesions recorded on the CRF, the date of tumor assessment should be derived as the earliest scan/assessment date. Since tumor assessments are captured on a log CRF page, a clustering algorithm for grouping scans will be used:

• Each cluster represents an actual unique assessment date. For each patient, the number of clusters is equal to the maximum number of unique assessment dates available among all target, non-target, new lesions and investigator overall assessment dates. SAS procedure, Proc Fastclus, is applied to a variable that represents the days from the date of treatment start to the date of the scan for each lesion/investigator overall assessment (date of scan – date of treatment start +1). Then the assessments of target and non-target lesions that occurred close to each other in time will be assigned to the same cluster

5.2.7. Sum of Lesion Diameters

For lesions that are assessed as 'too small to measure', 5 mm will be imputed and used in the calculation of the sum of the lesion diameters

DMB02-GSOP-RF02 4.0 Statistical Analysis Plan Template 01-Nov-2018 PFIZER CONFIDENTIAL Page 18 TMF Doc ID: 98.03

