#### 8.1. Efficacy Assessments

#### 8.1.1. Tumor Assessments

Tumor assessments will include all known or suspected disease sites. Computed tomography (CT) or MRI scans of Chest Abdomen Pelvis (CAP) and MRI of the brain will be performed at screening. Gadolinium contrast enhanced MRI must be used for assessment of CNS lesions with contingent slices of 1 mm for lesions 5 mm - 10 mm in size, 5 mm for lesions greater than 10 mm. Bone scans (or bone MRI if preferred by investigator) will be performed at baseline for all participants and repeated every 12 weeks on study only if evidence of bone metastases is observed at baseline (however, if a participant has bone involvement, assessment of those sites via appropriate modality is required every 6 weeks ±1 week up to 24 months or progressive disease whichever occurred first). For all tumor assessments, the method of assessment that was used at baseline should be the same method used throughout the study. CT and MRI scans to be done at every 6 weeks  $\pm 1$  week up to approximately 24 months (cycle 35) and then as per local clinical practice. Tumor assessment should be repeated at the end of treatment if more than 6 weeks have passed since the last evaluation. Tumor assessment should not be repeated at the end of treatment if progression occurs when the participant has shifted to the local clinical practice. Moreover, radiological tumor assessments will be conducted whenever disease progression is suspected (eg, symptomatic deterioration).

Assessment of response will be made using RECIST version 1.1 (Appendix 5). Confirmation of response will be required at least 4 weeks after initial response is observed.

All participants' files and radiologic images must be available for source verification and for peer/independent central radiology review as determined by the sponsor. Instructions for submission of these images will be provided in the Study Reference Manual.

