# Measurable Lesions

Lesions that can be accurately measured in at least one dimension (longest diameter in the plane of measurement is to be recorded) with a minimum size of:

- 10 mm for lesions other than lymph nodes and assessed by CT scan (CT scan slice thickness no greater than 5 mm)
- 10 mm for lesions assessed clinically by caliper measurement (lesions which cannot be accurately measured with calipers should be recorded as non-measurable).
- 20 mm for lesions assessed by chest X-ray.
- 15 mm in short axis for lymph nodes when assessed by CT scan (CT scan slice thickness recommended to be no greater than 5 mm).

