### **Non-measurable Lesions**

Non-measurable lesions include small lesions (longest diameter <10 mm or pathological lymph nodes with a  $\ge 10$  but <15 mm short axis) as well as truly non-measurable lesions. Truly non-measurable lesions include: leptomeningeal disease, ascites, pleural or pericardial effusion, inflammatory breast disease, lymphangitic involvement of skin or lung, abdominal masses identified by physical exam and not measurable by reproducible imaging techniques.

Nodes that have a short axis <10 mm are considered non-pathological and should not be recorded or followed.

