#### **Definition of Tumor Response**

#### **Target Lesions**

# Response in target lesions is defined as follows:

- Complete Response (CR): disappearance of all target lesions.
- Partial Response (PR): at least a 30% decrease in the sum of diameters of target lesions, taking as reference the baseline sum diameters.
- **Progressive Disease (PD):** at least a 20% increase in the sum of diameters of target lesions, taking as reference the smallest sum on study (this includes the baseline sum if that is the smallest on study). In addition to the relative increase of 20%, the sum must also demonstrate an absolute increase of at least 5 mm. The appearance of one or more new lesions is also considered a sign of progression.
- Stable Disease (SD): neither sufficient shrinkage to qualify for PR nor sufficient increase to qualify for PD, taking as reference the smallest sum diameters while on study.

When nodal disease is included in the sum of target lesions and the nodes decrease to 'normal' size (<10 mm), they may still have a measurement reported on scans. This measurement should be recorded even though the nodes are normal in order not to overstate progression should it be based on increase in size of the nodes. As noted earlier, this means that patients with CR may not have a total sum of 'zero' on the CRF.

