5.2.5. Measurable Disease

A patient will be considered to have measurable disease if there is at least one target lesion identified at baseline meeting the following criteria:

- Non lymph node lesions with longest diameter ≥ 10 mm by CT scan,
- Non lymph node lesions with longest diameter ≥ 10 mm caliper measurement by clinical exam,
- CNS lesions with longest diameter ≥5 mm provided by gadolinium contrast enhanced MRI perfomed with contingent slices of 1 mm, or
- Lymph nodes with short axis ≥ 15 mm when assessed by CT.

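### The 5 mm default for lesions too small to measure blocks a partial response in investigator-derived intracranial response when all brain targets are very small

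*SAP*

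**What the plan says.** SAP 5.2.7 has a single rule: when a lesion is assessed as too small to measure, "5 mm will be imputed and used in the calculation of the sum of the lesion diameters". It applies to all lesions and does not mention the brain.

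SAP 5.2.5 counts among measurable lesions "CNS lesions with longest diameter ≥5 mm provided by gadolinium contrast enhanced MRI", on 1 mm slices. Protocol 8.1.1 plans the imaging to match, with "contingent slices of 1 mm for lesions 5 mm - 10 mm in size". Small brain targets are thus an intended case. Protocol Appendix 5 differs: "Non-measurable lesions include small lesions (longest diameter <10 mm", with no CNS exception.

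Appendix 5 defines PR in target lesions as "at least a 30% decrease in the sum of diameters of target lesions, taking as reference the baseline sum diameters". It allows at most two targets per organ, and complete response (CR) is the disappearance of all targets.

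The two readings reach the analysis by different routes. Under SAP 5.2.6, investigator response is programmed from the target measurements on the CRF. Under SAP 6.1.1, best overall response by independent central review (ICR) is built from the responses that the radiologist reports. SAP 6.2.2 summarizes intracranial response in the same way as overall response, among participants with CNS metastases.

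**The concern.** A 5 mm default does no harm when lesions enter at 10 mm or more, because going from 10 to 5 mm is already a 50% fall. The SAP lowers the entry size for brain targets to 5 mm and leaves the default at 5 mm. The floor then equals the entry size, and a lesion that enters at 5 mm and becomes unmeasurable is scored as unchanged.

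This is a written rule that gives an incoherent ordering, so it is more than a missing detail. Greater shrinkage can earn a worse category. Intracranial response is named in the primary objective (Protocol 3 and 9.1), and Protocol 9.2 bases the response analysis on both overall and intracranial response. IC-TTR, IC-DoR and any waterfall or spider plot of sums that contain small brain targets use the same imputed value.

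**Working it through.** The documents give no figure on this point to reproduce: IC-ORR has no sample size, power or target.

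**Inputs.** Imputed value 5 mm (SAP 5.2.7). Smallest brain target 5 mm (SAP 5.2.5). PR if the current sum is at most 0.70 × the baseline sum (Protocol Appendix 5). At most two brain targets (Appendix 5).

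**Sole brain target, baseline b, imputed at 5 mm.** Change = (5 − b)/b. PR needs 5 ≤ 0.70b, so b ≥ 5/0.70 = 7.14 mm.

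| Baseline (mm) | Change when imputed at 5 mm | PR? |
|---|---|---|
| 5 | 0.0% | No |
| 6 | −16.7% | No |
| 7 | −28.6% | No |
| 7.15 | −30.1% | Yes |
| 8 | −37.5% | Yes |
| 10 | −50.0% | Yes |

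**Two brain targets, both imputed.** The sum becomes 10 mm, so PR needs a baseline sum of at least 10/0.70 = 14.29 mm. For 7 + 7 mm the change is (10 − 14)/14 = −28.6%, no PR. For 7 + 8 mm it is (10 − 15)/15 = −33.3%, PR.

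**Two brain targets, one imputed.** PR stays reachable if the other shrinks enough: 7 + 20 mm going to 5 + 10 mm is (15 − 27)/27 = −44.4%.

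**The reversal.** A 6 mm lesion recorded at 4.2 mm gives (4.2 − 6)/6 = −30%, a PR. The same lesion called too small to measure gives −16.7%, stable disease. SAP 6.1.1 needs two determinations of PR or better at least 4 weeks apart, so a measured PR followed by this call is not confirmed by that later assessment.

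**Direction.** I assume that a lesion called too small to measure is no larger than 5 mm. The imputed sum is then never below the true sum, so the rule can take a PR away but cannot create one.

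**Size.** One lost responder among N participants with CNS metastases costs 100/N points. The documents do not give N. For an assumed 20 to 40, this is 100/20 = 5.0 to 100/40 = 2.5 points each.

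**Effect on progression.** Progression needs a rise of at least 20% and at least 5 mm from the lowest sum. With a sole target, a true low of 2 mm gives progression at 7 mm, and an imputed low of 5 mm gives it at 10 mm. IC-DoR could therefore be lengthened among those who do count as responders.

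**A smaller value, 2.5 mm.** The PR threshold for a sole target becomes 2.5/0.70 = 3.57 mm, below the 5 mm entry size. Every sole brain target called too small to measure is then a PR, including a 5 mm lesion truly at 4 mm (−20%).

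**The case against.** The strongest reply is that the 5 mm value is a defensible convention and the situation is rare. Several parts of it stand.

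- A reader might infer that any brain target of about 7.1 mm or less is barred from PR. It is not. PR is judged on the sum, and a second brain target can carry it. Appendix 5 also selects targets by longest diameter, which makes all-small sets less likely.
- The rule applies only when a lesion is called too small to measure. As I read it, a recorded diameter below 5 mm is used as recorded, and complete disappearance still counts as CR. With 1 mm slices, many small residuals may have a recorded number.
- Stable disease is sometimes the right answer. For a 5 mm lesion, any residual above 3.5 mm is a fall of less than 30%.
- A reader might infer that IC-ORR by ICR is biased too. The documents do not support that: ICR response is taken as reported, and nothing says that SAP 5.2.7 governs the central read.
- The success criterion in SAP 5.1.2 concerns overall ORR, and IC-ORR has no threshold. Protocol 5.1 requires a measurable extracranial target, so overall response is little affected.
- Replacing 5 mm by 2.5 mm outright would be an error in the other direction, in a study without a control arm.

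These points narrow the scope. They do not remove the clash between a 5 mm entry size and a 5 mm floor, or the reversal that it produces.

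**Conclusion.** The concern holds for investigator-derived intracranial response. PR cannot be reached at an assessment where the sole brain target is imputed and its baseline was below 7.14 mm, or where two brain targets are both imputed and their baseline sum was below 14.29 mm. Given the assumption on residual size, any error in IC-ORR is downward. Its total size cannot be derived from the documents and is zero if no participant falls in this range.

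It may be tempting to conclude that the 10 mm minimum in Appendix 5 would cure the problem. It would remove the clash, but smaller brain lesions would become non-target lesions, for which Appendix 5 offers only CR, non-CR/non-PD or progression. PR based on those lesions alone would still be unavailable. Compared with Appendix 5, the SAP therefore loses no PRs; the fault is that its own two rules do not fit together.

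**What to change.** 1. In SAP 5.2.7, add a convention for brain targets of 5 to under 10 mm that are called too small to measure. Prespecify investigator-derived IC-ORR under both 5 mm and a smaller value, for example 2.5 mm. State that 5 mm can only lose PRs, while 2.5 mm scores every sole too-small-to-measure brain target as PR, so that the two results bracket the rate. The bracket is strict when all brain targets are imputed. It is not strict when one is measured: for 6 + 10 mm with the second measured at 9 mm, the PR limit is 0.70 × 16 = 11.2 mm; 2.5 mm gives 11.5 mm (no PR), and a true 1 mm residual gives 10 mm (PR).
2. State whether SAP 5.2.7 applies to the central read.
3. Reconcile the 5 mm CNS minimum in SAP 5.2.5 with the 10 mm minimum in Protocol Appendix 5, noting that a 10 mm limit does not restore PR for smaller brain lesions.

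The cost is a few lines of text and one extra derivation. The downside is that the smaller value is itself a convention and favours response, so it belongs in a sensitivity analysis and should not simply replace the 5 mm value.

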5.2.8. Adequate Baseline Tumor Assessment

Adequate baseline is defined using the following criteria:

- All baseline assessments must be within 28 days prior to and including the date of first dose.
- All documented lesions must have non-missing assessments (ie, non missing measurements for target lesions and non missing lesions status at baseline for non-target lesions).
- Measurable disease at baseline (see Section 5.2.5 for the definition of measurable disease)

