## 1.3. Schedule of Activities (SoA)

The schedule of activities table provides an overview of the protocol visits and procedures. Refer to Section 8 of the protocol for detailed information on each assessment required for compliance with the protocol.

The Investigator may schedule visits (unplanned visits) in addition to those listed in the schedule of activities table in order to conduct evaluations or assessments required to protect the well-being of the participant.

## 1.3.1. Screening and Cycle 1

Visit Identifier	Screening*	Cycle 1 (21 days)	Notes  *to be obtained within 28 days prior to registration
Visit Window	≤28 days	Day 1 (±1 day)	(X) refer to specific footnote when the measurement may be optional /repeat measurement might not be required.
Informed consent	X		Must be obtained prior to undergoing any study specific procedures that are not considered standard of care.
Tumor history	X		
Medical history	X		Data on prior anti-cancer therapy will be collected along with the best-known response from the previous ALK inhibitor.
Physical examination	X	X	
Weight	X	X	
Performance Status	X	X	
Contraception check (as appropriate)		X	
Laboratory	·		
Hematology	X	(X)	No need to repeat on C1D1 if baseline assessment performed within 7 days prior to that date. For those visits after C1D1, hematology labs should be performed according to lorlatinib product information.

Visit Identifier	Screening*	Cycle 1 (21 days)	Notes  *to be obtained within 28 days prior to registration
Visit Window	≤28 days	Day 1 (±1 day)	(X) refer to specific footnote when the measurement may be optional /repeat measurement might not be required.
Blood Chemistry	X	(X)	No need to repeat on C1D1 if baseline assessment performed within 7 days prior to that date. For those visits after C1D1, blood chemistry should be performed according to lorlatinib product information.
Pregnancy test	X	(X)	For female participants of childbearing potential, a serum or urine pregnancy test will be performed once at the start of screening and once at the baseline visit, immediately before study intervention administration. The pregnancy test should be performed at the clinical site's local laboratory.
Cardiac Monitoring	 		
12-lead ECG	X	(X)	No need to repeat on C1D1 if baseline assessment performed within 7 days prior to that date. During study treatment additional triplicate ECGs may be performed as clinically indicated and according to lorlatinib product information.

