LVEF Assessment	X		Echocardiogram or MUGA will be performed. During study treatment additional assessments may be performed as clinically indicated and according to lorlatinib product information.
			For France and Germany, a transthoracic echocardiogram (TTE) will be performed every 6 months (± 2 weeks) during treatment, and only at the end of treatment visit if the previous assessment was > 1 month. Pulmonary arterial pressure (PAP) will be assessed.
Registration	·		
Registration		(X)	Registration will be within 2 days prior to study treatment start.
Tumor Assessments			
CT and MRI Scan or Equivalent	X		Tumor assessments will include all known or suspected disease sites. CT or MRI scans of Chest Abdomen Pelvis [CAP] and MRI of the brain will be performed at screening. Bone scans (or bone MRI if preferred by investigator) will be performed at baseline for all participants and repeated every 12 weeks on study only if evidence of bone metastases is observed at baseline.

Visit Identifier	Screening*	Cycle 1 (21 days)	Notes  *to be obtained within 28 days prior to registration	
Visit Window	≤28 days	Day 1 (±1 day)	(X) refer to specific footnote when the measurement may be optional /repeat measurement might not be required.	
Cerebrospinal fluid if leptomeningeal/carcinomatous meningitis [LM/CM] disease is present	X		CSF is mandatory for participants who have asymptomatic radiologically suspected leptomeningeal disease (LM) or carcinomatous meningitis (CM) but negative spinal fluid.	
Other Clinical Assessments	Other Clinical Assessments			
Adverse Events	X	X	For AEs and SAEs, the active reporting period to Pfizer or its designated representative begins from the time that the participant provides informed consent, which is obtained prior to the participant's participation in the study through and including a minimum of 28 calendar days after the last administration of the study intervention. Refer to Section 8.3.1 for all specifications.	
Concomitant medications and non- drug supportive interventions	X	X		

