## 9.2. Sample Size Determination

The primary endpoint is Objective tumor response assessed by RECIST version 1.1 per ICR. Analysis of tumor response will be based on both Overall tumor response and on Intra-Cranial tumor response.

OR is defined as a confirmed CR or confirmed PR from the first dose of study treatment until disease progression, start of anticancer therapy or death due to any cause. Both CR and PR must be confirmed by repeat assessments performed no less than 4 weeks after the criteria for response are first met.

ORR is defined as the proportion of treated participants with confirmed CR or confirmed PR per ICR assessment and will be estimated together with its 2-sided exact 95% CI (using an exact Clopper-Pearson CI).

According to literature, platinum-based doublet chemotherapy in patients with ALK + NSCLC refractory to second generation TKIs has an objective response rate of approximately 30%. Setting as target for lorlatinib a response rate of about 43% (as observed in cohort EXP-3B of phase 2 portion of study B7461001), a sample size of 60 participants would result in an exact two-sided 95% CI of the ORR with lower limit of the CI greater than 30%. In order to compensate for a potential 15% drop out rate (participants with death prior to first post-baseline assessment, inadequate baseline assessment, new anticancer therapy started prior to first post-baseline assessment, post-baseline disease assessments missing), the overall sample size for the study is set to 70 participants.

The study will be considered to have met its primary endpoint if the lower limit of the 95% confidence interval around the estimated ORR excludes 30%.

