3. ENDPOINTS AND BASELINE VARIABLES: DEFINITIONS AND CONVENTIONS

3.1. Primary Endpoint

3.1.1. Confirmed OR by ICR

Objective Response (OR) based on ICR assessment is defined as complete response (CR) or partial response (PR) according to RECIST v1.1 from date of first dose until documented PD or start of new anti-cancer therapy without regard to discontinuation from treatment. Both CR and PR must be confirmed by repeat assessments performed no less than 4 weeks after the criteria for response are first met.

Participants without a CR or PR or with death prior to first post-baseline assessment, inadequate baseline assessment, new anti-cancer therapy started prior to first post-baseline assessment, and all post-baseline disease assessments missing will be considered as non-responders.

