3.4. Baseline Variables

The date of first dose (start date) of study treatment is the earliest date of non-zero dosing of the study drug. The date of last dose of study treatment is the latest date of non-zero dosing of the study drug.

No windowing will be applied when defining baseline, except as noted in Section 5.2.8 for tumor assessments. Any deviations from the protocol specified window will be documented as protocol deviations. A separate definition of adequate baseline will be provided for tumor assessment related efficacy endpoints.

For efficacy analyses and baseline characteristics associated with tumor assessments the last assessment prior to treatment start date will serve as the baseline assessment.

For Adverse Events the last assessment performed on or prior to date of the first dose of study treatment will serve as the baseline assessment. If there are no observations meeting these criteria, then baseline is considered missing.

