6.2.7. PFS by ICR/INV

Analysis set: ITT: All enrolled participants who take at least 1 dose of Lorlatinib

Analysis methodology:

PFS is defined as the time from date of first dose to the date of the first documentation of PD per RECIST v1.1 as assessed by ICR/INV or death due to any cause, whichever occurs first and will be summarized in months:

PFS (months) = [date of event or censoring-date of treatment start +1]/30.4375.

PFS data will be censored as follows:

- For participants who start a new anti-cancer therapy prior to an event, censoring will be at the last adequate tumor assessment (see Section 5.2.9) prior to the start of new anti-cancer therapy. Note: if date of progression occurs on the same date as the start of new anti-cancer therapy, the progression will be counted as an event.
- For participants with documented progression or death after two or more missing tumor assessments, censoring will occur at the last adequate tumor assessment prior to the missing assessments. In this study antitumor activity will be assessed through radiological tumor assessments conducted at screening and every 6 weeks until disease progression regardless of initiation of subsequent anti-cancer therapy. The allowable time window for disease assessments is ±1week while on treatment and whenever disease progression is suspected (eg, symptomatic deterioration). Therefore time without adequate assessment is defined as 98 days (12 weeks plus 2 weeks).
- For participants who do not have an adequate baseline tumor assessment or who do not have any post-baseline tumor assessments, censoring will occur on the date of first dose unless death occurred on or before the time of the second planned tumor assessment (ie, on or before day 98) in which case the death will be considered an event. Note for participants who died without any post baseline assessments and meet the definition of two or more missing assessment the reason for censoring will be documented as two or more missed assessments and censoring will occur on the date of first dose.
- All other participants alive without objective progression will be censored on the date of the last adequate tumor assessment.

DMB02-GSOP-RF02 4.0 Statistical Analysis Plan Template 01-Nov-2018 PFIZER CONFIDENTIAL Page 28 TMF Doc ID: 98.03 The date of tumor response at each nominal timepoint based on the ICR/INV assessments will be used for determining the dates of last adequate assessment for censoring purposes.

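### SAP 6.2.8 counts some early deaths as TTP events, against its own definition and tables and the protocol; as a minor point, SAP 5.2.8 rejects some baseline scans that the protocol allows

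*SAP*

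**What the plan says.** **TTP and early death.** SAP 3.2.8 and the opening of SAP 6.2.8 define TTP as time to first documented progression; death is not part of the endpoint. The third censoring bullet of SAP 6.2.8 repeats the PFS bullet of SAP 6.2.7, which begins "For participants who do not have an adequate baseline tumor assessment or who do not have any post-baseline tumor assessments, censoring will occur". That bullet censors at first dose, but makes a death on or before day 98 an event. SAP Table 4 has no such event: a participant without an adequate baseline is censored at first dose (first row), and a death within 98 days of first dose or of the last adequate assessment is censored at the date of death (third row). SAP Table 5 lists death as a reason for censoring. Protocol 9.4.1 censors deaths before progression at the date of death. For participants without an adequate baseline, or without an adequate post-baseline assessment in the first 12 weeks, it does so when death falls within 12 weeks.

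**Baseline window.** The protocol's Schedule of Activities requires screening procedures, including scans, "to be obtained within 28 days prior to registration", and adds: "Registration will be within 2 days prior to study treatment start". SAP 5.2.8 uses a different anchor: "All baseline assessments must be within 28 days prior to and including the date of first dose". SAP 3.4 says "Any deviations from the protocol specified window will be documented as protocol deviations" and, for tumor data, that "the last assessment prior to treatment start date will serve as the baseline assessment". Under SAP 3.1.1, participants with "inadequate baseline assessment, new anti-cancer therapy started prior to first post-baseline assessment, and all post-baseline disease assessments missing will be considered as non-responders".

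**The concern.** The TTP sentence fits PFS, where death is an event, but not TTP. As written, the same participant can be an event or be censored, depending on whether the programmer follows the text or the table. That choice should not be left until data are in hand.

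The window mismatch feeds the same rule, because an inadequate baseline is one of its two triggers, and it also reaches the primary endpoint. A site that follows the protocol exactly can produce a baseline scan that the SAP calls inadequate. That participant is a non-responder whatever the later scans show, and is censored at first dose for PFS and TTP unless the early-death exception applies. Because the SAP bullet covers every baseline assessment, one early image among CT, brain MRI and bone scan is enough.

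**Working it through.** **1. TTP: the rules side by side.** Take a death by day 98 without documented progression.

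| Source | No adequate baseline | Adequate baseline, no post-baseline assessment |
|---|---|---|
| SAP 6.2.8, third bullet | Event | Event |
| SAP 3.2.8 definition | Not an event | Not an event |
| SAP Table 4, first row | Censored at first dose | Does not apply |
| SAP Table 4, third row | Censored at death | Censored at death |
| Protocol 9.4.1, death within 12 weeks | Censored at death | Censored at death |

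The first group has three possible outcomes and the second has two. PFS Table 2 attaches a death footnote to its no-baseline row; TTP Table 4 has none.

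Table 5 adds a labelling problem. Death ranks seventh, below no adequate baseline (first) and no adequate post-baseline assessment (sixth, when an end-of-study page is present). These participants can therefore be censored at death yet reported under another reason.

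The limits differ too: 12 weeks = 84 days in the protocol against 98 days in the SAP. Deaths on days 85 to 98 fall outside the protocol's special rule but inside the SAP's.

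**2. TTP: size.** The documents give no count of such deaths, so this is per death. With about 70 at risk, one death counted as an event multiplies the Kaplan-Meier curve from then on by 1 - 1/70, a relative fall of 1.4%. The fall in the 12-month rate S is S/70. For assumed S of 30%, 50% and 70%, that is 0.43, 0.71 and 1.00 points.

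**3. Baseline window.** Let s be days from scan to registration (at most 28) and r days from registration to first dose (at most 2). The protocol allows s + r up to 30; SAP 5.2.8 allows 28. The compliant combinations that fail are (s, r) = (28, 1), (27, 2) and (28, 2), which are study days -29, -29 and -30. The mismatch needs a scan at the end of the window and registration 1 or 2 days before dosing.

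**4. Primary endpoint: the plan's figure first.** The exact two-sided 95% lower limit is 30.6% for 26/60 (43.3%) and 29.1% for 25/60. This reproduces the statement in protocol 9.2 that 60 participants at about 43% give a lower limit above 30%. For the allowance, 60/0.85 = 70.6, against the stated 70.

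At N = 70, the lower limit is 31.1% for 30/70 and 29.8% for 29/70. Success needs at least 30 responders.

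Let k of the 70 be made non-responders by the window. The documents do not give k; 1 and 2 are assumptions.

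| k | Loss of expected ORR at 43% (43 × k/70) | P(Bin(70-k, 0.43) ≥ 30) | P(Bin(70-k, 0.30) ≥ 30) |
|---|---|---|---|
| 0 | 0 | 55.5% | 1.5% |
| 1 | 0.61 points | 51.4% | 1.2% |
| 2 | 1.23 points | 47.2% | 1.0% |

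**The case against.** On TTP, the intent is clear: the definition, both tables and the protocol all treat death as censoring, and the sentence looks carried over from PFS. TTP is a descriptive secondary endpoint with no hypothesis test, and both documents let the SAP modify the protocol outside the primary endpoint. All of this stands. It limits the consequence but leaves the instruction wrong. The move from 12 weeks to 98 days is a change the SAP may make; it only needs recording.

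On the window, SAP 3.4 announces a separate definition of adequate baseline for tumor endpoints, so compliance and analytic adequacy may differ by design. Anchoring scan age to first dose is also defensible. That stands as a principle, but nothing in the SAP explains why scans the protocol accepts should cost a participant a response.

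Three stronger readings are tempting.

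- A reader might infer that every early death becomes a TTP event. The sentence covers only participants with no adequate baseline or no post-baseline assessment.
- A reader might infer that the window could create a false success. It only turns participants into non-responders, so it works against success.
- A reader might infer that SAP 5.2.8, which names no reader for measurable disease, lets a central read discard documented progressions. SAP 5.2.9 derives post-baseline adequacy by reader, SAP 6.5.1 summarises measurability by both readers, and protocol inclusion criterion 4 requires a measurable extracranial lesion. The documents do not support treating this as an error.

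**Conclusion.** The TTP sentence is wrong as written and should be corrected before database lock. It affects only a narrow group. Each such death moves the 12-month TTP rate by about 0.4 to 1.0 points, assuming about 70 at risk and a rate between 30% and 70%.

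The window mismatch is real but minor. The number affected is unknown and probably very small; the only related figure is protocol 9.2, "In order to compensate for a potential 15% drop out rate", which covers all non-evaluable reasons together. The success rule is a hard threshold, so one lost responder matters at exactly 30 of 70. At a true 43%, losing 1 or 2 participants costs about 4 or 8 percentage points of success probability. At a true 30%, the chance of a false success falls slightly. These figures depend on the assumed counts and are not forecasts.

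**What to change.** **SAP 6.2.8.**

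- In the third bullet, replace the clause making an early death an event with: *in which case TTP is censored on the date of death*.
- Add a footnote to the first row of Table 4 saying the same for deaths up to 98 days after first dose.
- Make the Table 5 reason for these participants agree with their censoring date.
- Record the 98-day limit as a change from the protocol's 12 weeks.

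**SAP 5.2.8.** Reword the first bullet: *All baseline assessments must be within 30 days before, and prior to, the date of first dose.* This covers every protocol-compliant scan and agrees with SAP 3.4, which takes the last assessment before treatment start. It also avoids the reading in which a 28-day span that includes the dosing day would exclude day -28. Anchoring to registration instead would leave scan age before dosing unlimited if registration were early.

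**Cost.** A few lines of SAP text, one footnote and small programming changes; the sample size stays at 70. The downside is accepting scans up to 2 days older, an age the protocol already permits. Where registration was too late for such a scan to be compliant, SAP 3.4 would still record a deviation.
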